9.2 Secondary Efficacy Data and Endpoints

Additional efficacy data is stated below that will be collected for this study and how it will be analyzed. Specific secondary efficacy endpoints are described how they will be derived for each analysis visit.

9.2.1 NRS Score Assessing Worst Pain Intensity in the Past 24 Hours

The collection method of the NRS score assessing worst^[10] pain intensity in the past 24 hours is the same as the primary efficacy data described in Section 9.1 for the NRS score assessing average pain intensity in the past 24 hours. The study-issued handheld devices were not programmed with logic checks to flag instances in which subjects might have mistakenly reported their worst pain intensity scores as being less than their average pain intensity scores. However, rather than assume these to be self-evident errors and thus correct them, such scores will be analyzed based on the actual values collected.

The secondary endpoints of interest with this data is the change in the mean score from baseline to each analysis week of treatment (Weeks 1, 2, 3, and 4). The same analyses methods will be applied to the NRS score assessing worst pain intensity in the past 24 hours as described in Sections 9.1, 9.1.1, and 9.1.2. No imputation methods for missing data will be applied for this secondary endpoint.

The actual means, change from baseline, and percent change from baseline will be summarized using descriptive statistics. ANCOVA analyses using the mean change from baseline will be provided for Weeks 1, 2, 3, and 4 as described in Section 5.3.5.2. A MMRM model will be analyzed for all post-baseline analysis visits (Weeks 1, 2, 3, and 4) for the mean change from baseline as described in Section 5.3.5.3.

9.2.2 Change in the Mean NRS Score Assessing Average Pain Intensity in the Past 24 Hours at Weeks 1, 2, 3, and 4

This is the same data described in Section 9.1 for the NRS score assessing average pain intensity in the past 24 hours. The secondary endpoints of interest with this data is the change in the mean score from baseline to each analysis week of treatment (Weeks 1, 2, and 3). The same analyses methods will be applied to Weeks 1, 2, and 3 as described in Section 9.1.2 for Week 4.

ANCOVA analyses using the mean change from baseline will be provided for individual models for Weeks 1, 2, and 3 as described in Section 5.3.5.2. A MMRM model will be analyzed for all postbaseline analysis visits (Weeks 1, 2, 3, and 4) for the mean change from baseline as described in Section 5.3.5.3. No imputation methods for missing data will be applied for the MMRM model.

9.2.3 NRS Score Assessing Average Pain upon Walking Intensity in the Past 24 Hours

The collection method of the NRS score assessing average pain upon walking intensity in the past 24 hours is the same as the method for the primary efficacy data described in Section 9.1 for the NRS score assessing average pain intensity in the past 24 hours. The secondary endpoints of interest with this data is the change in the mean score from baseline to each analysis week of treatment (Weeks 1, 2, 3, and 4). The same analyses methods will be applied to the NRS score assessing average pain upon walking intensity in the past 24 hours as described in Sections 9.1, 9.1.1 and 9.1.2. No imputation methods for missing data will be applied for these secondary endpoints.

The actual means, change from baseline, and percent change from baseline at each analysis visit will be summarized using descriptive statistics. ANCOVA analyses using the mean change from baseline will be provided for individual models for Weeks 1, 2, 3, and 4 as described in Section 5.3.5.2. A MMRM model will be analyzed for all post-baseline analysis visits (Weeks 1, 2, 3, and 4) for the mean change from baseline as described in Section 5.3.5.3.

9.2.4 Patient Global Impression of Change (PGI-C)

The PGI-C is a 7-point Likert scale that allows subjects to rate the change in the disease state from study initiation to specific time points during the study or at the end of the study. It provides the subject's impression of overall change since beginning the study. Below are the numeric values assigned in the 7-point scale along with categorical values and analysis categorical values[4]:

Numeric Value	Categorical Value	Analysis Categorical Value
1	Very Much Improved	Improved
2	Much Improved	Improved
3	Minimally Improved	Minimally Improved to Worse
4	No Change	Minimally Improved to Worse
5	Minimally Worse	Minimally Improved to Worse
6	Much Worse	Minimally Improved to Worse
7	Very Much Worse	Minimally Improved to Worse
Missing	Missing	Minimally Improved to Worse

The secondary endpoints of interest are the actual collected values at Weeks 2 and 4. The last post-baseline visit for each subject will also by summarized. There is no baseline collection due to the nature of this data being the change after receiving study drug.

Descriptive statistics will be provided using the numeric value data for each analysis visit. A frequency distribution will be created for each analysis visit based on the collected categorical values. The analysis categorical values stated above will be summarized by frequency distributions, odds ratio, and relative risk analyses described in Section 5.3.5.5.

9.2.5 Short-Form McGill Pain Questionnaire, version 2 (SF-MPQ-2)

The SF-MPQ-2 measures the sensory, affective, and evaluative qualities of pain, including symptoms relevant to neuropathic pain. The tool includes visual analogue as well as verbal rating scales of pain intensity on a total of 22 neuropathic and non-neuropathic pain descriptors that are each evaluated on a 10-point numerical rating scale/Likert scale ranging from 0 to $10^{[12]}$. Where 0 represents none and 10 is worst possible.

The following questions that make up each published summary scale score [13]:

- Continuous Descriptors:
 - Throbbing Pain, Cramping Pain, Gnawing Pain, Aching Pain, Heavy Pain, and Tender
- Intermittent Descriptors:
 - Shooting Pain, Stabbing Pain, Sharp Pain, Splitting Pain, Electric-Shock Pain, and Piercing
- Neuropathic Descriptors:
 - Hot-Burning Pain, Cold-Freezing Pain, Pain Caused by Light Touch, Itching, Tingling or 'Pins and Needles', and Numbness
- Affective Descriptors:
 - o Tiring-Exhausting, Sickening, Fearful, and Punishing-Cruel

Each of the 4 summary scale scores will be calculated by the mean if more than 50% of the responses are available for the calculation. For example, the Continuous Descriptors summary scale score will need at least 4 of the 6 components available in order to calculate the mean. If all the 4 summary scale scores can be calculated, then the total pain score is computed by averaging the non-rounded 4 individual summary scale scores. If at least one summary scale score is missing, the total pain score will be set to missing. Each mean summary scale and total pain score will take on values ranging from 0 to 10 and will be rounded off by one number after the decimal point.

The secondary endpoints of interest with this data are the published summary scales and total pain scores change from baseline to Week 4. Subjects will be instructed to answer each question based on the pain and related symptoms they felt during the past week, so responses should be interpreted as cumulative over that time period. The SF-MPQ-2 will be assessed at the Baseline and Week 4/Early Termination visits.

The actual means and change from baseline will be summarized using descriptive statistics. ANCOVA analyses using the change from baseline to Week 4 will be provided for the published summary scales and total pain scores. The change from baseline to last post-baseline visit for each subject will also by summarized.

Protocol No.: NYX-2925-2001

9.2.6 Norfolk Quality of Life Questionnaire - Diabetic Neuropathy (QOL-DN)

The Norfolk QOL-DN is a 47-item, subject-reported questionnaire designed to measure the relationship between symptomatic diabetic neuropathy and quality of life from the perspective of the patient. It is composed of 2 parts: questions related to symptoms experienced by the subject and questions related to the impact of the subject's neuropathy on activities of daily life. As a comprehensive questionnaire it addresses the entire spectrum of neuropathy including the concentration of symptoms in the extremities, subtle loss of function such as fine motor impairments and sensory changes, unique problems with proprioception and balance, and autonomic symptoms that are not captured in existing instruments. An initial biographical page collects twelve health-related background history items, which are not scored. These are followed by 35 scored questions - numbered items comprising the entire scale^[14]. Lower scores represent a better quality of life. Each individual question concerns particular functions or symptoms related to the following 5 subscale domains^[15, 16]:

• Symptoms:

- Questions 1-7 for Symptoms in the following Categories: Numbness; Tingling, Pins and Needles; Electric Shocks; Other Unusual Sensations; Superficial Pain; Deep Pain; Weakness
 - 5 Possible Responses: Feet, Legs, Hands, Arm, or None
 - For "None" selected, a score of 0 will be assigned to that question. Otherwise, a score of each location response selected will be assigned a value of 1. As a result, each question may have a score of 0 or 1 for each location, with a total maximum of 4.
- O Question 9: "In the past 4 weeks, has the touch of bed sheets, clothes, or wearing shoes bothered you?"
 - 5-point Likert scale ranging from 0 ("Not a problem") to 4 ("Severe problem")
 - The symptoms subscale score is the sum of the 8 questions with scores ranging from 0 to 32.
- Activities of Daily Living (ADLs):
 - o Questions 12, 22, 23, 25, and 26
 - 5-point Likert scale ranging from 0 ("Not a problem") to 4 ("Severe problem")
 - The ADLs subscale score is the sum of the 5 questions with scores ranging from 0 to 20.
- Small Fiber Neuropathy:
 - o Questions 10, 16, 17, and 18
 - 5-point Likert scale ranging from 0 ("Not a problem") to 4 ("Severe problem")
 - The small fiber neuropathy subscale score is the sum of the 4 questions with scores ranging from 0 to 16.
- Physical Functioning/Large Fiber Neuropathy:
 - o Questions 8, 11, 13-15, and 24
 - 5-point Likert scale ranging from 0 ("Not a problem") to 4 ("Severe problem")

Protocol No.: NYX-2925-2001

- Questions 27-30 and 33-35
 - 5-point Likert scale ranging from 0 ("Not at all") to 4 ("Severely")
- o Question 31
 - Excellent = -2; Very Good = -1; Good = 0; Fair = 1; Poor = 2
- Ouestion 32
 - Much Better = -2; Somewhat Better = -1; About the Same = 0; Somewhat Worse = 1; Much Worse = 2
- The physical functioning/large fiber neuropathy subscale score is the sum of the 15 questions with scores ranging from -4 to 56.
- Autonomic Neuropathy:
 - O Questions 19, 20, and 21
 - 5-point Likert scale ranging from 0 ("Not a problem") to 4 ("Severe problem")
 - The autonomic neuropathy subscale score is the sum of the 3 questions with scores ranging from 0 to 12.

If 4 or more (>10%) responses are missing from the 35 questions, then the subject will be excluded from the Norfolk QOL-DN analyses. If 3 or fewer responses are missing, then the following data imputations will be performed:

- If any missing questions occurred during the Baseline visit, then the mean score for all subjects in at that specific study site will be used to impute missing questions.
- If any missing questions occurred during a post-baseline visit, then the mean score for all subjects in that specific randomized treatment group will be used to impute missing questions.

The Total Quality of Life Score will be calculated by the sum of all the 35 questions stated above in the subscale domains with the total score ranging from -4 to 136.

The questionnaire has been validated using factor analysis and its psychometric properties defined. It has tested at the 90th percentile for reliability, sensitivity and specificity. It correlates with other measures of neuropathy, most strongly with the total neuropathy score (TNS) (r=0.53, p=0.0001) and then with the neuropathy score in the lower limbs (NIS-LL+7) (r=0.27, P=0.0005), but not with individual indices of electrophysiology or quantitative sensory testing. Of the QOL subscales, Activities of Daily Living (ADLs) were the greatest contributors to the total neuropathy score. Norfolk QOL-DN has been used in major neuropathy clinical trials for diabetic neuropathy.

The secondary endpoints of interest with this data is the published subscale domains and total scores change from baseline to Week 4. The Norfolk QOL-DN is sensitive to the different features of diabetic neuropathy including small fiber, large fiber, and autonomic nerve function. Subjects will be instructed to rate most items over the last 4 weeks, so responses should be interpreted as cumulative over that time period. Not merely an inventory of the subject's status at the moment of filling out the questionnaire. The Norfolk QOL-DN will be assessed at the Baseline and Week 4/Early Termination visits.

The actual means and change from baseline will be summarized using descriptive statistics. ANCOVA analyses using the mean change from baseline will be provided for Week 4. The change from baseline to last post-baseline visit for each subject will also by summarized.

All 35 individual question responses, calculated subscale domain scores, and the total score will be presented in subject listings. All other health-related questions answered on the front page of the questionnaire will be presented in subject listings, but not in summary tables.

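### The QOL-DN missing-item limit is counted over all 35 questions, which suits the total score but not the five domain scores that are also endpoints

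*SAP*

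**What the plan says.** SAP 9.2.6 defines five domains, each a sum of its own items, and a total over all 35 questions. Both levels are endpoints: "The secondary endpoints of interest with this data is the published subscale domains and total scores change from baseline to Week 4". Protocol 5.3.1 names the subscale scores only.

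The rule for using a questionnaire works on the 35-question count alone. Above the limit: "If 4 or more (>10%) responses are missing from the 35 questions, then the subject will be excluded from the Norfolk QOL-DN analyses". Below it: "If 3 or fewer responses are missing, then the following data imputations will be performed". Missing baseline items are filled at site level ("the mean score for all subjects in at that specific study site will be used to impute missing questions"). Missing post-baseline items are filled at arm level ("the mean score for all subjects in that specific randomized treatment group will be used to impute missing questions"). No minimum number of answers per domain is given. The smallest domain has three items: "The autonomic neuropathy subscale score is the sum of the 3 questions with scores ranging from 0 to 12".

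SAP 5.1.5 computes a change score when the values are present or imputed, so a filled domain goes into the ANCOVA like any other.

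The SAP's other instruments with subscales have limits per scale. For the SF-MPQ-2 (SAP 9.2.5): "Each of the 4 summary scale scores will be calculated by the mean if more than 50% of the responses are available for the calculation". HADS (9.2.8) allows at most three of seven items missing per subscale. BPI-DPN (9.2.10) needs three of four Severity items and four of seven Interference items.

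**The concern.** The rule that decides whether a domain score is formed does not look at how much of that domain was answered. It can go wrong in two directions. A form with three blanks all in one short domain yields a score made mostly or wholly of other patients' averages. A form with four blanks loses all five domain scores, including those the patient completed in full.

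The baseline fill has a separate weakness. A study-site mean has no value at a site with no other answered form. It is also unstable at small sites, and SAP 4.7 removes site from the models precisely because some sites enrol few subjects.

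At stake is the accuracy and the sample size of one family of secondary endpoints. The primary pain endpoint does not use this questionnaire.

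**Working it through.** **Reproducing the plan's own figures.** From the item lists in SAP 9.2.6: 8 + 5 + 4 + 15 + 3 = 35, with each question used once. Maxima: 32 + 20 + 16 + 56 + 12 = 136, as stated. 3/35 = 8.6% and 4/35 = 11.4%, so the label of more than 10% fits a limit of four. The missing-item count is taken per visit; the SAP does not say so.

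**Direction 1: up to three missing, all filled.** Largest imputed share of a domain = min(3, items)/items. The last column applies the SAP's SF-MPQ-2 rule to each domain.

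| Domain | Items | Largest imputed share | Fewest answered | Needed for more than 50% |
|---|---|---|---|---|
| Autonomic | 3 | 3/3 = 100% | 0 | 2 |
| Small fiber | 4 | 3/4 = 75% | 1 | 3 |
| Activities of daily living | 5 | 3/5 = 60% | 2 | 3 |
| Symptoms | 8 | 3/8 = 37.5% | 5 | 5 |
| Physical functioning/large fiber | 15 | 3/15 = 20% | 12 | 8 |

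Only the autonomic domain can be empty and still be scored.

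**Direction 2: exactly four missing, subject excluded.** Four blanks touch at most four of five domains, so at least one is always complete. Enumerating all 52,360 ways to miss four of 35 questions:

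- Four domains complete in 1,441 patterns, three in 16,643, two in 27,256 and one in 7,020.
- With more than 50% answered required per domain, all five stay scorable in 47,568 patterns (47,568/52,360 = 90.8%), four in 4,774 and three in 18. The current rule keeps none.

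For example, four blanks among the large-fiber items leave 11 of 15 answered there, yet four complete domains (35 − 15 = 20 answered items) are dropped.

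**How often.** The documents give no item-missing rate. Assume, for illustration, that items go missing independently with probability p.

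- Excluded: P(X ≥ 4), X ~ Binomial(35, p).
- Autonomic empty, the rest complete: p³(1 − p)³². The expected count uses 600 forms (300 subjects × 2 visits).

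| p | Forms excluded | Per 300 at one visit | P(autonomic empty) | Expected in 600 forms |
|---|---|---|---|---|
| 2% | 0.5% | 1.5 | 0.0000042 | 0.003 |
| 3% | 2.0% | 6.1 | 0.000010 | 0.006 |
| 5% | 9.6% | 28.7 | 0.000024 | 0.015 |

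In simulated excluded forms, about 42% to 44% of domain scores are complete and about 98% have more than half their items answered. Among retained forms, only 0.06% to 0.25% of domain scores have half or fewer answered. Under independence, then, the practical loss is almost all in direction 2.

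**Baseline fill.** 300 subjects over 39 sites (SAP 5.7) is 300/39 = 7.7 per site on average, and fewer at low-enrolling sites. The SAP gives no fallback where a site mean cannot be formed.

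**The case against.** A whole-form completeness limit is a legitimate choice. It is natural for the total, which the SAP lists as an endpoint, and the SAP sets its rules by instrument: ISI (9.2.7) tolerates no missing item at all. This stands for the total. It does not explain why a complete domain should be dropped because of blanks elsewhere.

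A reader might infer that autonomic scores without patient data will be common. The documents do not support that. Under independent missingness the expected number is well below one. Questions 19 to 21 are consecutive, so a skipped block would produce such a score, but nothing in the documents says this happens.

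A reader might also infer that filled values are passed off as observed. The SAP openly calls them imputations; the accurate statement is that they enter the ANCOVA on the same footing as answered items.

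A third inference, that some sites have one subject and the baseline fill must fail, is also unsupported. The documents report low enrolment at some sites, not site counts.

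SAP 5.1.4 keeps baseline subscale scores when a total cannot be calculated, which sits badly with whole-subject exclusion. It does nothing for Week 4 domains.

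Two objections to a remedy have force. A per-domain 50% rule tolerates more missing data: 3 + 2 + 1 + 7 + 1 = 14 of 35 items (40%) could be blank with all five domains scored, against 8.6% now. And the subject's own domain mean cannot serve as the fill for large fiber, where questions 31 and 32 run from −2 to 2 and the other 13 items from 0 to 4. A subject with 4 on all 13, 2 on question 32 and question 31 blank would be given (52 + 2)/14 = 3.86, and a domain sum of 57.9 against a maximum of 56.

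**Conclusion.** The point holds in a limited form. One limit over 35 questions is appropriate for the total and poorly matched to the five domains. Both errors follow directly from the SAP text. How often they occur is unknown. At assumed independent missing rates of 2% to 5%, the main effect is loss of usable domain scores in about 0.5% to 9.6% of questionnaires, and the upper figure depends on the 5% assumption. Clustered skipping would change both figures.

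This concerns a secondary instrument in a phase 2 study, and SAP section 13 does not mark the QOL-DN tables for the topline analyses. No bias in any treatment comparison has been shown. The change is worth making because it is cheap, keeps reported data and follows the SAP's own practice for its other subscales.

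**What to change.** In SAP 9.2.6:

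1. Form each domain score when more than 50% of that domain's items are answered at the visit; otherwise set only that domain to missing. This means 5 of 8 Symptoms, 3 of 5 activities of daily living, 3 of 4 small fiber, 8 of 15 large fiber and 2 of 3 autonomic items.
2. Keep the limit of three or fewer missing of 35 for the Total Quality of Life Score only.
3. For missing baseline items, replace the study-site mean by that item's baseline mean over all randomized subjects, pooled across sites and arms. Do not use the subject's own domain mean, given the different scoring of questions 31 and 32.
4. State that the count is per visit, say what fills post-baseline items in scorable domains (the arm mean stays unless changed), and align SAP 5.1.4 with the result.

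The cost is a few sentences and minor programming before database lock. The number of subjects may differ between domains and the total, and some large-fiber scores may rest on as few as 8 of 15 answered items. Reporting the number of imputed items per domain and arm would show whether that matters.

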5.3.5.2 Analysis of Covariance Model

Using the change from baseline as a dependent variable, an analysis of covariance (ANCOVA) model with treatment (200 mg of NYX-2925, 50 mg of NYX-2925, 10 mg of NYX-2925, and Placebo) as the main effect and the baseline value as a covariate will be used to compare treatment groups at an individual analysis visit^[4]. The comparison of the NYX-2925 versus placebo will be assessed by forming the least squares means estimate of each particular NYX-2925 treatment groups stated in Section 5.2 and comparing them to the placebo group. The Kenward-Roger approximation will be used to estimate denominator degrees of freedom. Here is the SAS® code:

PROC MIXED DATA=ADAM ORDER=DATA METHOD=REML;

CLASS TRTP;

MODEL CHG = BASE TRTP / DDFM=KENWARDROGER;

LSMEANS TRTP / DIFF CL ALPHA=0.05;

/* -1 = Placebo; 0 = 10 mg of NYX-2925; 0.5 = 200 mg and 50 mg of NYX-2925 */

LSMESTIMATE "200 mg and 50 mg of NYX-2925 versus Placebo" TRTP 0 0.5 0.5 -1 / CL;

RUN:

The following ANCOVA model statistics for each treatment group will be presented in an analysis table:

- n =the number of records for that treatment or pooled treatment group
- Least Squares Mean for the treatment groups
- Standard Error for the treatment groups
- Least Squares Mean Difference for the NYX-2925 treatment groups versus Placebo
- Standard Error Difference for the treatment groups versus Placebo
- 95% Confidence Interval for the Difference for the treatment groups versus Placebo
- P-value for the Difference for the treatment groups versus Placebo

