9.2.8 Hospital Anxiety and Depression Scale (HADS)

The HADS is a self-reported screening tool for anxiety and depression in non-psychiatric clinical populations. The scale consists of 14 items (7 each for anxiety and depression), each rated on a 4-point scale ranging from 0 to 3 (i.e. 0 = not at all; 3 = most of the time). The categorical responses are slightly different for some of the questions, but the numeric scores remained the same from 0 to 3. Responses are based on the relative frequency of symptoms over the preceding week^[19].

When a HADS questionnaire is partially incomplete, the individual subscale scores are estimated by assuming that the missing item(s) have a value equal to the average of those in existence, provided that no more than 3 items of a subscale are missing [20]. The individual imputed missing scores will use the specific subscale mean score and will be rounded off to the nearest whole number. If an individual subscale score is missing 4 or more items, then that subscale score will be set to missing. A total score adding the anxiety and depression subscale scores for HADS will not be calculated.

Possible scores range from 0 to 21 for each subscale. An analysis of scores on the 2 subscales supported the differentiation of each mood state into 4 ranges^[21]:

- Normal Cases (Scores 0-7)
- Mild Cases (Scores 8-10)
- Moderate Cases (Scores 11-14)
- Severe Cases (Scores 15-21)

The secondary endpoints of interest with this data is the published subscale and total scores change from baseline to Week 4. Subjects will be instructed to answer each question based how they have felt in the past week, so responses should be interpreted as cumulative over that time period. The HADS will be assessed at the Screening, Baseline, and Week 4/Early Termination visits.

The actual means and change from baseline will be summarized using descriptive statistics. ANCOVA analyses using the mean change from baseline will be provided for Week 4. The change from baseline to last post-baseline visit for each subject will also by summarized. The 4 interpreted categorical values for each subscale will be summarized in a frequency distribution table and a shift table.

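### Filling missing post-baseline QOL-DN items with the randomized arm's mean gives false precision, negligible to small for the total score but possibly material for the short subscales

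*SAP*

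**What the plan says.** SAP 9.2.6 limits missing items over the whole questionnaire: "If 4 or more (>10%) responses are missing from the 35 questions, then the subject will be excluded from the Norfolk QOL-DN analyses". With 3 or fewer missing, the rule depends on the visit. At baseline, "then the mean score for all subjects in at that specific study site will be used to impute missing questions". After baseline, "then the mean score for all subjects in that specific randomized treatment group will be used to impute missing questions".

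The limit is not repeated by subscale, and the subscales differ greatly in length. The shortest is described thus: "The autonomic neuropathy subscale score is the sum of the 3 questions with scores ranging from 0 to 12". Small fiber neuropathy has 4 items, activities of daily living 5, symptoms 8 and physical functioning/large fiber 15.

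The endpoints are the five subscales and the total: "The secondary endpoints of interest with this data is the published subscale domains and total scores change from baseline to Week 4". On the analysis, the section says "ANCOVA analyses using the mean change from baseline will be provided for Week 4". The model in SAP 5.3.5.2 has treatment "as the main effect and the baseline value as a covariate will be used to compare treatment groups at an individual analysis visit". It is fitted once to one completed dataset. The multiple-imputation, LOCF and BOCF sensitivity analyses in SAP 9.1.3 cover only the primary NRS endpoint, so nothing corrects the QOL-DN variance.

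Other questionnaires are handled within the subject. For HADS (SAP 9.2.8), subscale scores are "estimated by assuming that the missing item(s) have a value equal to the average of those in existence". SF-MPQ-2 (9.2.5) and BPI-DPN (9.2.10) average the subject's answered items above a minimum count, and ISI (9.2.7) sets the total to missing.

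**The concern.** Deterministic filling from the arm mean does two things to a treatment comparison. It reduces the scatter within each arm, because the filled values lie at its centre. It also keeps the filled subjects in the sample size as though they had supplied data. Both shrink the reported standard error, while the real uncertainty still depends only on the answers actually given. Confidence intervals are then too narrow and the test rejects too often when there is no effect.

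How far this goes depends on how much of a score is filled. Three items out of 35 are a small share of the total. The same three can be the whole autonomic subscale or three quarters of the small fiber subscale, and both are secondary endpoints with their own ANCOVA p-values.

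**Working it through.** **The plan's own figure.** The SAP gives no power or precision figure for QOL-DN. Its one power figure is for the primary NRS endpoint (SAP 4.4: 75 per arm, difference 1.05, SD 2.25, two-sided 0.05, about 80%). It reproduces: 81.5% by the normal approximation and 81.0% by the noncentral t.

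**Inputs.** From the SAP: 75 subjects per arm and four arms (4.3, 4.4); two-sided alpha 0.05 (5.6); at most 3 of 35 items filled (3/35 = 8.6%; 4/35 = 11.4%, consistent with the stated 10% limit); a 3-item autonomic subscale (9.2.6). The item-missing rate is not given, so a range is used.

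**Closed form, whole subscale filled.** Let a fraction *f* of each arm have the entire subscale filled, with *n* subjects per arm and variance σ².
- True variance of the arm mean, which rests on the *n*(1 − *f*) observed subjects: σ²/[*n*(1 − *f*)].
- Reported variance, because the filled subjects add almost nothing to the residual sum of squares but are counted in *n*: about σ²(1 − *f*)/*n*.
- Reported SE / true SE = √[(1 − *f*)²] = 1 − *f*.
- Actual type I error = 2[1 − Φ(1.96(1 − *f*))].

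| Filled per arm of 75 | *f* | SE ratio | 1.96(1 − *f*) | Type I error |
|---|---|---|---|---|
| 2 | 0.027 | 0.973 | 1.908 | 5.6% |
| 4 | 0.053 | 0.947 | 1.855 | 6.4% |
| 8 | 0.107 | 0.893 | 1.751 | 8.0% |

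This is approximate once baseline is in the model, so it was checked by simulation.

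**Simulation of the SAP's ANCOVA.** Change was regressed on baseline and four arms, with 75 per arm and 35 items scored 0 to 4. Assumptions: inter-item correlation 0.4, latent baseline-to-Week 4 correlation 0.6, items missing completely at random, and each gap filled with the arm's mean for that item at that visit (the SAP does not say that its mean is taken this way). There were 3,000 null runs per case, so type I error is known to about ±0.8 points. Full data gave 4.8% to 5.2%.

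| Score | Subjects affected | Reported/true SE | Type I error |
|---|---|---|---|
| Total, 3 random items filled | 5% | 1.001 | 4.6% |
| Total | 10% | 0.988 | 5.5% |
| Total | 20% | 0.977 | 5.7% |
| Total | 100% (extreme bound) | 0.909 | 7.5% |
| Autonomic, all 3 items filled | 5% | 0.955 | 6.0% |
| Autonomic | 10% | 0.889 | 8.1% |
| Autonomic | 20% | 0.792 | 12.2% |

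The closed form gives 6.3%, 7.8% and 11.7% for the three autonomic rows, which agrees within simulation error.

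**Is the estimate shifted?** With a true effect added (800 runs per case), the mean estimated difference in the total was −12.7 to −13.1 with filling and −12.9 with full data. For the autonomic subscale it was −1.09 to −1.10 with filling and −1.09 to −1.12 with full data. No shift is visible.

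**Comparison with filling from the subject's own answers.** With every subject missing 3 items, filling from the mean of the subject's answered items gave an SE ratio of 1.005 and a type I error of 5.0% for the total, against 0.909 and 7.5% for the arm mean. This run averaged over all of the subject's answered items, so it supports the principle and is not a test of the exact subscale rule proposed below.

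**The case against.** The strongest reply is that the table of 2, 4 and 8 subjects is a corner case. It needs that many subjects in every arm to skip all three autonomic questions and nothing else, and 8 of 75 is 10.7% of an arm. If only one of the three items is missing, a separate simulation (6,000 null runs, error about ±0.6 points) gave 5.3% with 4 subjects per arm and 5.8% with 8. The total is hardly touched at modest missingness. QOL-DN is one of ten secondary endpoint bullets in protocol 5.3.1, SAP 5.6 makes no formal multiplicity adjustment, and the primary result is unaffected. All of this stands. It limits the size of the point but does not remove the fault.

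Three stronger readings are tempting, and the documents do not support them.
- **That the rule biases the treatment difference toward the arm means.** Filled values do carry the observed arm difference, but its expectation is unchanged when items are missing completely at random. The fault is in the precision.
- **That needing treatment codes to build the scores threatens the blind.** SAP 4.6 has the SAP final before database lock and the codes released after it. The multiple imputation for the primary endpoint in SAP 9.1.3 also uses the planned arm.
- **That the site-mean rule at baseline does harm.** It differs from the post-baseline rule, but it uses no treatment information and no effect on the comparison has been shown. Aligning the two is a matter of consistency.

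It is also fair to say that the SAP sets missing-item rules instrument by instrument, so the contrast with HADS does not by itself show the QOL-DN rule to be wrong. It shows that a within-subject rule is already accepted practice in this plan.

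**Conclusion.** The point holds as a minor one about false precision. SAP 9.2.6 analyses arm-mean values as if observed, and nothing elsewhere in the SAP corrects for it. The effect on the 35-item total is undetectable with 5% of subjects affected and small at 10% to 20%. For the 3-item autonomic subscale, the worst case of 2, 4 or 8 fully filled subjects per arm makes the standard error 2.7%, 5.3% or 10.7% too small and puts type I error at about 5.6%, 6.4% or 8.0%. Partial filling of a subscale does less.

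These figures assume 75 per arm, equal filling across arms and items missing completely at random. How often subjects skip QOL-DN items is unknown from the documents, so the figures show a possible range and do not predict what this trial would see. If missingness depended on the unseen answers, the estimate itself could also move; that was not examined.

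**What to change.** Replace the two filling rules in SAP 9.2.6 with one within-subject rule, applied at Week 4 and, for consistency, at baseline:
- If at least half of a subscale's items are answered, replace each missing item with the subject's own mean of the answered items in that subscale.
- Let all items scored 0 to 4 serve as donors for one another, including Q9 with Q1–7. Add 2 to Q31 and Q32 when they serve as donors, and subtract 2 from the fill when either is the missing item, so that their −2 to 2 range is kept.
- If fewer than half are answered, set that subscale and the total to missing.

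Treating the 0-to-4 items as interchangeable and shifting Q31 and Q32 matters because Q9, Q31 and Q32 each have response categories unlike the rest of their subscale. A rule restricted to identical response formats would leave them with no donor.

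The cost is SAP wording and a few missing scores. If the existing limit of 3 missing items stays, a subscale is lost only when 2 or 3 of the 3 autonomic items, 3 of the 4 small fiber items, or 3 of the 5 daily-living items are blank. Symptoms (at least 5 of 8 answered) and physical functioning (at least 12 of 15) are never lost. In the losing cases the total is lost as well, although at least 32 of its 35 items were answered.
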